5.5.3 Additional Safety Assessments

5.5.3.1 Clinical laboratory evaluations

The protocol-required laboratory parameters collected within UP0073 are given in [Table 5-9](#). All non-protocol-required laboratory parameters will not be presented in any tabulated summaries, but will be listed.

Table 5-9: Protocol-required Laboratory Assessments

Laboratory Assessment	Parameters
Hematology	Platelet count
	Red blood cell count
	Hemoglobin
	Hematocrit
	Red blood cell indices – Mean corpuscular volume, Mean corpuscular hemoglobin, % reticulocytes.
	White blood cell count with differentials – Neutrophils, Lymphocytes, Monocytes, Eosinophils, Basophils
Clinical Chemistry	Blood urea nitrogen
	Potassium
	Aspartate Aminotransferase/Serum Glutamic-Oxaloacetic Transaminase
	Total and direct bilirubin
	Creatinine

Table 5-9: Protocol-required Laboratory Assessments

Laboratory Assessment	Parameters
	Sodium
	Alanine Aminotransferase/Serum Glutamic-Pyruvic Transaminase
	Total Protein
	Glucose (fasted)
	Calcium
	Alkaline Phosphatase
Routine Urea	Specific gravity
	pH, glucose, protein, blood, ketones, bilirubin, urobilinogen, nitrite, leukocyte esterase by dipstick
	Microscopic examination (if blood or protein is abnormal)
	Renal biomarker analysis
Other screening tests	Follicle-stimulating hormone (FSH) and estradiol (as needed in women of non-childbearing potential only)
	Urine drug screen (to include at minimum: amphetamines, barbiturates, cocaine, opiates, cannabinoids, methadone, and benzodiazepines)
	Serum and urine human chorionic gonadotropin (hCG) pregnancy test (as needed for women of childbearing potential)
	Serology (HIV antibody, HBsAg and hepatitis C virus antibody)

5.5.3.1.1 Laboratory values over time

Laboratory variables and changes from Baseline will be summarized using descriptive statistics for Part A by time point, and sequence, and for Part B by time point, and sequence. A by-participant listing will be provided for the SS.

Measurements that are below the limit of quantification (BLQ) or above the limit of quantification (ALQ) will be presented as BLQ or ALQ in the listings. For the purpose of calculating change from Baseline or for descriptive statistics, BLQ values will be imputed with half of the lower limit of quantification (LLoQ) and ALQ values will be imputed to the upper quantification limit.

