#### **4.1.2 Part B**

Part B of this study is an ethnobridging study evaluating the safety, tolerability, and PK of a single oral dose of UCB0599 at 3 dose levels (90mg, 180mg, and 360mg) under normal gastric pH conditions in healthy participants of Japanese and Chinese origins. Each group of ethnic origin (N=15 total for each) will be randomized to a 4-treatment, 6-sequence, 2-period crossover study using UCB0599:placebo in a 4:1 ratio, as shown below and in the Study Schema ([Figure 1-1](#)). Sequence 6 will only commence after Sequence 5 has been completed for all 4 participants. Sequences 3 and 4 (Cohort 3) will only commence after Sequences 1 and 2 (Cohort 2) have been

completed for all 5 participants; Sequences 5 and 6 (Cohort 4) will only commence after Sequences 3 and 4 have been completed for all 5 participants allowing the SMC review to be carried out before the start of Sequence 5.

- Sequence 1: placebo 90mg, followed by placebo 180mg (N=1)
- Sequence 2: UCB0599 90mg followed by UCB0599 180mg (N=4)
- Sequence 3: placebo 180mg, followed by placebo 360mg (N=1)
- Sequence 4: UCB0599 180mg, followed by UCB0599 360mg (N=4)
- Sequence 5: placebo 360mg, followed by placebo 90mg (N=1)
- Sequence 6: UCB0599 360mg, followed by UCB0599 90mg (N=4)

See Section 3 for more details on the objectives and endpoints of the study.

No participant will ever receive both UCB0599 and placebo, and therefore no intra-participant comparison will be possible; the crossover aspect of the Part B design refers to the dose level over 2 periods in order to limit the number of participants to be recruited into this study. This design will allow the collection of UCB0599 data at each dose level for 8 study participants of each ethnic origin and the collection of dose-matching placebo data for 2 study participants of each ethnic origin for each dose. Participants will be blinded to the treatment (ie, UCB0599 or placebo), but not to the dosage within a sequence.

Part B consists of the following periods (for a total duration of up to 45 days):

- A 28-day Screening Period (2 to 28 days before administration of study medication)
- 2 treatment periods (for a total duration of up to 10 days)

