### **9.5 Planned safety and other analyses**

#### **9.5.1 Safety analyses**

Unless stated otherwise, all safety analyses will be performed on the SS.

All AEs will be coded using the most recent Medical Dictionary for Regulatory Activities (MedDRA®) and characterized as pretreatment and treatment emergent according to the intake of the study medication.

The occurrence and incidence of TEAEs will be summarized by MedDRA system organ class (SOC), HLT, and preferred term (PT), and by treatment and ethnic group (for Part B only). The occurrence and incidence of TEAEs will also be summarized by maximum event intensity and by relationship to the study medication. Adverse events will be categorized by severity (mild/moderate/severe). All AEs will be listed and will include actions taken for each AE, the time of onset of the AE after dosing, and the duration of each AE. Adverse events leading to discontinuation and SAEs will also be summarized by treatment group and ethnic group.

Laboratory variables and changes from Baseline will be summarized by time point and will be presented by treatment and ethnic group. For categorized values according to the reference range, shift tables from Baseline (Day -1, or Day 1 prior to first treatment) to each post-Baseline

time point will be presented for selected variables to be defined in the SAP. Values outside the reference range will be flagged in the listings.

Vital sign variables (SBP and DBP, pulse rate, respiration rate, and body temperature) and changes from Baseline (Day -1, or Day 1 prior to first treatment) will be summarized by time point and will be presented by treatment and ethnic group.

Single 12-lead ECGs will be recorded at each time point as noted in the study Schedule of Activities (Section 1.3). Descriptive statistics will be presented for ECG values and changes from Baseline (Day -1, or Day 1 prior to first treatment) over time.

See Section 9.8 for details on planned interim analyses and data monitoring.

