5.1.1.4 Definition of Analysis by Variables

Table 5-3: Definition of Analysis by Variables for Part A

Term	Variables
Sequence	Sequence 1 (ABC)
	Sequence 2 (ACB)
	Sequence 3 (BCA)
	Sequence 4 (BAC)
	Sequence 5 (CAB)
	Sequence 6 (CBA)
Formulation	180mg (90mg x 2 granules in capsule)
	180mg non-encapsulated tablet containing PPD
	180mg encapsulated tablet containing PPD
Gastric condition	Normal gastric pH
	Elevated gastric pH

Note: A: 180mg (90mg x 2 granules in capsule) current clinical formulation (reference formulation); B: 180mg non-encapsulated tablet containing PPD ; C: 180mg encapsulated tablet containing PPD .

Table 5-4: Definition of Analysis by Variables for Part B

Term	Variables
Sequence	Sequence 1 (C=1, J=1; 90mg → 180mg)
	Sequence 2 (C=4, J=4; 90mg → 180mg)

Table 5-4: Definition of Analysis by Variables for Part B

Term	Variables
	Sequence 3 (C=1, J=1; 180mg → 360mg)
	Sequence 4 (C=4, J=4; 180mg → 360mg)
	Sequence 5 (C=1, J=1; 360mg → 90mg)
	Sequence 6 (C=4, J=4; 360mg → 90mg)
Dose level	Pooled Placebo
	90mg
	180mg
	360mg
Participant group	Japanese participants
	Chinese participants
	Part A healthy participants under normal gastric pH condition on the formulation chosen for Part B

C=Chinese participants; J=Japanese participants.

Table 5-5: Analysis Performed by “by Variables”

Analysis	Part A by Variable	Part B by Variable
Disposition	Sequence	Sequence
Medical History		
Concomitant Medications		
Important Protocol Deviations		
PK Concentration	Formulation and gastric condition	Dose level and participant group
Adverse Events	Formulation	Dose level and participant group
Laboratory Values	Time Point and Sequence	Time Point Sequence
Vital Signs		
ECG		

ECG= electrocardiogram; PK=pharmacokinetic.

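### The SAP groups Part B laboratory tables by randomisation sequence, so none separates Japanese from Chinese participants, and it does not specify the protocol's shift tables

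*SAP*

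**What the plan says.** Protocol 9.5.1 sets the grouping: "Laboratory variables and changes from Baseline will be summarized by time point and will be presented by treatment and ethnic group". For values categorised by reference range it adds "shift tables from Baseline (Day -1, or Day 1 prior to first treatment) to each post-Baseline" assessment, and says which analytes this covers: "time point will be presented for selected variables to be defined in the SAP".

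SAP 5.5.3.1.1 instead groups the laboratory summaries "for Part A by time point, and sequence, and for Part B by time point, and sequence". The laboratory row of SAP Table 5-5 agrees: its Part A cell reads "Time Point and Sequence", and its Part B cell holds the same two variables. SAP Table 5-4 shows that a sequence contains both origins, for example "Sequence 2 (C=4, J=4; 90mg → 180mg". Participant group is a separate by-variable in that table. Table 5-5 applies it to Part B PK concentrations and adverse events, but not to laboratory values.

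For Part B vital signs (SAP 5.5.3.2.1) and ECG (SAP 5.5.3.3.1), the SAP text uses dose level and participant group at each time point. For laboratory data the SAP plans descriptive statistics and a by-participant listing. It mentions no shift table and lists no variables for one. SAP 6.4 declares no changes to the protocol-planned analyses.

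**The concern.** Part B is an ethnobridging study, and its design is justified in Protocol 4.1.2 by the numbers it yields in each origin: "This design will allow the collection of UCB0599 data at each dose level for 8 study participants of each ethnic origin". Change from Baseline in laboratory data is one of its listed safety endpoints. If the SAP is followed as written, a reader of the report finds no table of laboratory change in Japanese participants, none in Chinese participants, and no single summary for any one dose. The placebo reference is spread over three columns too small to be useful. With no shift tables specified, no table counts participants who move outside the reference range.

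The protocol's word for treatment cannot reasonably be read as sequence. The note to Protocol Table 1-2 lists the four treatments as placebo and the three UCB0599 doses. Even on that reading, ethnic group would still be missing. Document versions do not appear to explain the difference either: the SAP is based on the 02 Mar 2023 protocol, and the Amendment 1 summary of changes lists none for Section 9.5.1.

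**Working it through.** **Inputs.** Participants per origin by sequence (Protocol 4.1.2): sequences 1, 3 and 5 (placebo) have 1 each; sequences 2, 4 and 6 (active) have 4 each. Part B laboratory days (Protocol Table 1-4): Screening, Day -1, Day 5, Day 10 and Safety Follow-Up (SFU). Dosing is on Days 1 and 6.

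**Plan's own figures.** Per origin, 1 + 4 + 1 + 4 + 1 + 4 = 15, and 2 × 15 = 30. Each dose occurs in two active and two placebo sequences:

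| Dose | Day 5 follows it in | Day 10 follows it in | Active per origin | Matching placebo per origin |
|---|---|---|---|---|
| 90 mg | Seq 2 (placebo: Seq 1) | Seq 6 (placebo: Seq 5) | 4 + 4 = 8 | 1 + 1 = 2 |
| 180 mg | Seq 4 (placebo: Seq 3) | Seq 2 (placebo: Seq 1) | 4 + 4 = 8 | 1 + 1 = 2 |
| 360 mg | Seq 6 (placebo: Seq 5) | Seq 4 (placebo: Seq 3) | 4 + 4 = 8 | 1 + 1 = 2 |

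The protocol's 8 active and 2 placebo per dose and origin are reproduced.

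**Cells under the SAP rule (sequence and study day).** There are three active columns of 4 Japanese + 4 Chinese = 8, and three placebo columns of 1 + 1 = 2. Check: 3 × 8 + 3 × 2 = 30. Every column mixes the origins. Each active cell holds 4 of the 8 observations planned for that dose in each origin; the other 4 sit in another column on the other day.

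**Cells by dose level and origin.** The result depends on how time point is defined.

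- *Study days kept separate.* On any one day a dose comes from a single active sequence, so the active cell is n = 4 per dose and origin. Pooled placebo is 1 + 1 + 1 = 3 per origin.
- *Day relative to the period's dose.* By the SAP 5.1.1.1.1 formula, Day 5 is 5 − 1 + 1 = 5 and Day 10 is 10 − 6 + 1 = 5; SAP Table 5-1 places both at Relative Day +5. Merged, the active cell is 4 + 4 = 8 per dose and origin. Pooled placebo is 3 participants with 3 × 2 = 6 observations per origin. Check: 3 × 8 + 6 = 30 = 15 × 2.

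As an illustration of precision, the 95% half-width for a mean, in SD units, is t(0.975, n − 1)/√n. It is 1.59 at n = 4 and 0.84 at n = 8, so keeping the days separate widens the interval by a factor of 1.59/0.84 ≈ 1.9. The SAP plans no such interval for laboratory data.

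**Part A.** On-treatment laboratory tests are on Day 14 and Day 33 only (Protocol Table 1-3). Day 14 follows three formulations and Day 33 follows six doses. No Part A sample follows one formulation alone, so grouping by formulation is not feasible and the regrouping is confined to Part B.

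**The case against.** Several points on the other side stand and set the limits of this finding.

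- A reader might infer that the tables hide dose altogether. They do not: sequence and day together identify the last dose given, as the table above shows. What is missing is the split by origin and a single summary per dose.
- A reader might infer that Part B's primary safety assessment is compromised. Its primary safety endpoints are three incidences of treatment-emergent adverse events, and SAP 5.5.2 tabulates adverse events by dose level and group. Laboratory change is listed among the other safety endpoints.
- There are partial safeguards. Clinically relevant laboratory changes are recorded as adverse events (Protocol 8.2.4), potential Hy's Law cases are listed by dose level and ethnic group (SAP 6.1.6), and a by-participant laboratory listing is planned. None of these replaces a summary table.
- A reader might infer that the shift tables were deliberately withdrawn. The SAP is silent on them and refers to table shells that are not part of these documents. What can be said is that it does not name the variables delegated to it.
- A reader might take Table 5-5 to prescribe sequence for vital signs and ECG as well. Those cells are blank in the available text and only appear to share the laboratory entry; the SAP text for both is in order.
- Sequence grouping has one merit. Laboratory Baseline is a single value before the first dose (SAP Table 5-2), so the Day 10 change follows both doses, and sequence keeps that order visible. This is a reason to keep a sequence table as a supplement, but it does not justify leaving out origin.

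**Conclusion.** The concern holds for Part B. A stated SAP rule contradicts Protocol 9.5.1, differs from the SAP's own text for vital signs and ECG, and is not declared as a change. Followed as written, it gives no laboratory table by origin, splits each dose over two columns, and divides placebo into three columns of 2. Separately, the SAP leaves the shift tables and their variables unspecified.

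The consequence is a deficiency in the planned summary tables for a non-primary safety endpoint. No data are lost, and the primary adverse-event tables are unaffected. The counts assume the planned enrolment with every participant completing both periods. The figure of 8 per dose and origin also assumes that Day 5 and Day 10 are merged as one post-dose time point; otherwise it is 4.

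**What to change.** 1. In SAP 5.5.3.1.1 and the laboratory row of Table 5-5, summarise Part B by time point relative to the period's dose, dose level received in that period (placebo pooled) and participant group. Restrict participant group to the Japanese and Chinese levels, since Part A has no laboratory sample specific to one formulation. Day 5 goes to the Period 1 dose and Day 10 to the Period 2 dose.
2. State how the two observations from each placebo participant are handled, and to which dose the SFU visit is assigned.
3. Footnote that Period 2 change is measured from the single Baseline before the first dose and so follows both doses. The sequence table may be kept as a supplement.
4. Add the protocol's shift tables with the variables named, or declare and justify their removal in SAP 6.4.
5. Clarify the vital sign and ECG rows of Table 5-5 so that they match SAP 5.5.3.2.1 and 5.5.3.3.1.

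The cost is SAP wording and table shells. No new data or assessments are needed.

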5.5.3.2 Vital Signs

Supine vital signs measured within UP0073 include:

- Pulse rate
- Systolic blood pressure

- Diastolic blood pressure
- Respiratory rate
- Tympanic body temperature

Vital signs will be measured in triplicate. The mean values will be calculated and recorded on the CRF.

Reference ranges for each vital sign will be recorded on the CRF. Clinically significant abnormalities will be flagged in the listings.

5.5.3.2.1 Vital Sign Values Over Time

The vital sign variables and changes from Baseline will be summarized using descriptive statistics for Part A by time point, gastric condition ,and formulation, and for Part B by time point, dose level, and participant group. A listing will be provided for the SS.

5.5.3.3 Electrocardiograms

The following ECG parameters will be obtained:

- Heart rate (beats/min),
- PR-interval (msec [milliseconds]),
- QRS-duration (msec),
- QT-interval (msec),
- QTcF (QT corrected for heart rate using Fridericia's formula) (msec),
- Investigator's conclusion on ECG profile.

5.5.3.3.1 Electrocardiogram Values Over Time

The electrocardiogram results and changes from Baseline will be summarized using descriptive statistics for Part A by time point, gastric condition, and formulation, and for Part B by time point, dose level, and participant group. A by-participant listing will be provided for the SS.

The following cut-points in QTcF based on the mean of the triplicate data will be summarized categorically (number and percentage of participants).

For observed data:

- <450 msec
- ≥ 450 to <480 msec
- ≥ 480 to <500 msec
- ≥ 500 msec

For change from Baseline in QTcF:

- <30 msec
- ≥ 30 to <60 msec
- ≥ 60 msec "

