**Table 1-3: Part A Schedule of activities**

Procedure	Screening	Treatment Period 1—6 a													SFU b / ETV
		In-Clinic Period													
	D-28 to D-2	D-1	D1	D2 to D5	D6	D7 to D10	D11	D12 to D18 c	D19	D20 to D23	D24	D25 to D28	D29	D30 to D33	Day 37 (± 2 days)

c The blood pregnancy test will be done at the Screening Visit and the urine pregnancy test will be done on all other occasions.

f Blood hematology and chemistry laboratory tests will be obtained in the fasting state following an overnight fast of at least 10 hours. Urinalysis includes standard analysis, microscopy, and renal biomarker analysis. For the AKI biomarkers, analysis should be performed on the fresh urine sample. Spot analysis will be performed on either fresh urinalysis sample or 24 hours urine sample, as noted.

g Only performed on Day 14 and Day 33.

h A COVID-19 test will take place per site standard to allow flexibility in the event the COVID-19 response plan changes throughout the study (ie, frequency of testing).

i During the Screening Period, at Baseline (only if the ECG was done more than 3 days before screening [between D-28 and D-2, inclusive]), and on Day 1, the 12-lead ECG (single recordings) will be performed after a rest of at least 10 minutes predose and 2 hours after dosing. If there are abnormalities that are considered clinically significant for a particular study participant, ECG recordings will be performed in triplicate at 2- to 3-minute intervals (3 ECGs within a 5-minute timeframe) prior to the exclusion of the participant (Section 7.1.2).

j Systolic and diastolic blood pressure, respiration rate, pulse rate, and tympanic body temperature will be assessed. Vital signs will be performed after a rest of at least 5 minutes predose, then 30 min, and 2 hours after study medication dosing on Day 1, Day 6, Day 11, Day 19, Day 24, and Day 29. Vital signs (to be taken before blood collection for laboratory tests) will consist of 3 pulse rates and 3 blood pressure (BP) measurements (3 consecutive BP readings will be recorded at intervals of at least 1 minute).

k An IRT will be used for assigning eligible participants to a treatment regimen based on a predetermined production randomization and/or packaging schedule provided by UCB (or designee) (Section 6.3).

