**Table 1-4: Part B Schedule of Activities**

Procedure	Screening	Treatment Period 1				Treatment Period 2			SFU a /ETV
		In-Clinic Period				In-Clinic Period			
	D-28 to D-2	D-1	D1	D2-4	D5	D6	D7-9	D10	D13 (±2 days)
Genetic blood sampling			X i						
Meals j		X	X k	X	X	X k	X	X	
Confinement		X	X	X	X	X	X	X l	

AE=adverse event; AKI=acute kidney injury; BMI=body weight index; COVID-19=Coronavirus Disease 2019; D=Day; ECG=electrocardiogram; ETV=Early Termination Visit; HBsAg=hepatitis B surface antigen; HCV=hepatitis C virus; HIV=human immunodeficiency virus; PCR= polymerase chain reaction; PK=pharmacokinetic(s); QD=once daily; SFU=Safety Follow Up

a An SFU Visit is planned after 7 days of the last study medication administration. Participants who prematurely withdraw from the study will have the ETV as soon as possible after the time of withdrawal, and will have all SFU procedures performed.

b The blood pregnancy test will be done at the Screening Visit and the urine pregnancy test will be done on all other occasions.

c Blood hematology and chemistry laboratory tests will be obtained in the fasting state following an overnight fast of at least 10 hours. Urinalysis includes standard analysis, microscopy, and renal biomarker analysis. For the AKI biomarkers, analysis should be performed on the fresh urine sample. Spot analysis will be performed on either fresh urinalysis sample or 24 hours urine sample, as noted.

d A COVID-19 test will take place per site standard to allow flexibility in the event the COVID-19 response plan changes throughout the study (ie, frequency of testing).

e 12-lead ECGs (single recordings) will be performed during the Screening Period, at Baseline (only if the ECG was done more than 3 days before screening [between D-28 and D-2, inclusive]), Day 1 (after a rest of at least 10 minutes predose and 2 hours after dosing), Day 2 (24 hours postdose), Day 6 (after a rest of at least 10 minutes predose and 2 hours after dosing), Day 7 (24 hours postdose), and the SFU Visit. If there are abnormalities that are considered clinically significant for a particular study participant, ECG recordings will be performed in triplicate at 2- to 3-minute intervals (3 ECGs within a 5-minute timeframe) prior to the exclusion of the participant (Section 7.1.2).

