## **8.2.3 Electrocardiograms**

Single 12-lead ECG recordings will be obtained as outlined in the Schedule of Activities in Section 1.3 for Part A ([Table 1-3](#)) and Part B ([Table 1-4](#)) using an ECG machine that automatically calculates the pulse rate and measures PR, QRS, QT, and QTcF intervals. Refer to Section 7.1.2 for QTcF withdrawal criteria and any additional QTc readings that may be necessary.

The study participant should be resting in the supine position for at least 10 minutes before the start of the recordings.

The Investigator should review all ECG recordings and, if there are abnormalities that are considered clinically significant for a particular study participant, then the Investigator should initiate a review by a specialist of all ECG data pertaining to that study participant. The following ECG parameters will be recorded in the eCRF: heart rate, PR-interval, QRS-duration, QT-interval, QTcF, and Investigator's conclusion on ECG profile.

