Derived variables in general will display the mean, sd, median, and IQR to 1 more decimal place than the variables used in the derivation. If the number of decimal places reported in the raw data is varied then use either the maximum raw number of reported decimal places or 3, whichever is the lowest, as a guide for the descriptive statistics. If participants have more than one observation for a given time point, the observation closest to the intended time point will be used. If both observations are equidistant from the intended time point, then the later value will be used.

Refer to Appendix 2 (Section 6.2.1 and Section 6.2.2) for standard reporting procedures of PK concentrations and parameters in listings, tables, and figures.

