5.1.1.7 Handling of repeated and unscheduled measurements

All repeated and unscheduled measurements will be presented in the data listings, where applicable. Repeated measurements are defined as more than 1 measurement at same time point. The following general rules will apply to all repeated and unscheduled measurements:

- For repeated measurements obtained prior to the first dose of study medication the latest value (which may be scheduled or unscheduled) will be used in the calculation of the descriptive statistics.
- For repeated measurements obtained for the designated Baseline value, the latest value (which may be scheduled or unscheduled) will be defined as the Baseline provided that this occurred prior to the first dose of study medication.
- Unscheduled measurements and repeated measurements after the first one at a given time point will not be used in the descriptive statistics at time points after first dose of study medication.
- Unscheduled measurements performed for the Early EOS/WD visit will be assigned to the EOS Visit and analyzed accordingly as an EOS Visit.

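### The SAP defines its QTcF category tables on the mean of triplicate ECGs, but every scheduled ECG is a single recording, so read literally no scheduled ECG qualifies

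*SAP*

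**What the plan says.** SAP 5.5.3.3.1 first plans descriptive statistics for ECG values and changes from Baseline, and a by-participant listing. It then adds categorical QTcF summaries: "The following cut-points in QTcF based on the mean of the triplicate data will be summarized categorically". The sentence introduces both sets of categories, one for observed values (cut-points 450, 480 and 500 msec) and one for change from Baseline (30 and 60 msec).

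The protocol describes the recordings differently.

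- Section 8.2.3: "Single 12-lead ECG recordings will be obtained as outlined in the Schedule of Activities in Section 1.3".
- Table 1-3 footnote on ECGs (Part A): "the 12-lead ECG (single recordings) will be performed after a rest of at least 10 minutes predose and 2 hours after dosing".
- Table 1-4 footnote on ECGs (Part B): "12-lead ECGs (single recordings) will be performed during the Screening Period, at Baseline", followed by the other scheduled time points.
- Section 9.5.1 also describes the ECGs at each time point as single.

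Both footnotes and Section 7.1.2 call for triplicates only when an abnormality is considered clinically significant for a particular participant.

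The SAP has two general rules for more than one value at a time point. Section 5.1 takes the observation closest to the intended time, with a tie-break: "If both observations are equidistant from the intended time point, then the later value will be used". Section 5.1.1.7 says, for time points after the first dose: "Unscheduled measurements and repeated measurements after the first one at a given time point will not be used in the descriptive statistics".

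**The concern.** The table is defined on a type of measurement that the trial does not routinely collect. A programmer must either follow the text, which leaves nearly everyone out of the categories, or depart from it without a written rule. The usual departure would be to use the single value where there is no triplicate. Participants with a triggered set would then be summarised by a mean and everyone else by one reading.

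The participants affected are those whose ECG an investigator found abnormal enough to repeat. Protocol 2.3 names cardiac effects as an important potential risk, and change from Baseline in the 12-lead ECG is an endpoint in Part B. The basis of the table should therefore be fixed before the data are seen. With 8 participants on active drug per dose and ethnic group, moving one participant between categories shifts a percentage by 1/8 = 12.5 points. This assumes that the categories are shown by dose level and participant group, as the ECG descriptive statistics in the same section are.

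**Working it through.** The plan gives no figure to reproduce. The check is a comparison of texts and a count of scheduled recordings.

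**1. Which scheduled ECGs are triplicates?** None. Protocol 8.2.3, 9.5.1 and the footnotes to Tables 1-3 and 1-4 all specify single recordings. The assessment scheduled in triplicate is vital signs (Protocol 8.2.2, SAP 5.5.3.2).

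**2. How many scheduled post-Baseline ECGs are there?** Inputs are planned enrolment from Protocol 4.1 (42 in Part A, 30 in Part B) and the time points in Tables 1-3 and 1-4. Full enrolment and no dropout are assumed, and Part B replacements are not counted.

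- Part A: Day 1 at 2 hours and the SFU Visit, so 42 × 2 = 84.
- Part B: Day 1 at 2 hours, Day 2, Day 6 predose, Day 6 at 2 hours, Day 7 and the SFU Visit, so 30 × 6 = 180.
- Total: 84 + 180 = 264. Number that meet the SAP definition: 0.

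**3. What is the Baseline for the change categories?** SAP Table 5-2 lists a single 12-lead ECG. Its Baseline cell is read here as shared with vital signs, that is, predose on Day 1. So there is no scheduled triplicate Baseline, and even a triggered post-dose triplicate would normally be compared with a single reading.

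**4. What happens to the percentages?** Under SAP 5.1 the default denominator is the number of participants in the analysis set. Read literally, a participant without a triplicate counts in the denominator and falls in no category.

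**5. What do the SAP rules give for a triggered post-dose set?**

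| SAP section | Value used |
|---|---|
| 5.5.3.3.1 (QTcF categories) | mean of the triplicate |
| 5.1.1.7 (general) | first recording at the time point |
| 5.1 (general) | recording closest to the intended time; the later one if tied |

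The two general rules agree only when the first recording is also strictly the closest. No sentence says which of them prevails.

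**6. Is the departure declared?** No. SAP 6.4 records no change to protocol-planned analyses.

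**The case against.** **The intended input is clear.** SAP Table 5-2 and Protocol 9.5.1 both say single, so a sensible programmer would use the single values. This stands in part: an empty or highly selected table follows from the literal text and is not a certain outcome. It does not remove the problem, because the SAP would still be silent on which value to use for a triggered set.

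**A specific rule may override a general one.** This is fair for 5.5.3.3.1 against 5.1.1.7, so it would be too strong to say that three rules conflict on an equal footing. The disagreement between the two general rules, 5.1 and 5.1.1.7, remains.

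**The SAP predates Protocol Amendment 1.** This does not explain the mismatch. The amendment's stated purpose is to add the capsule option for Part B, and its listed changes include none to the ECGs.

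**Little depends on this table.** This stands. The categories are an SAP addition to the descriptive statistics that Protocol 9.5.1 requires, and those statistics and the listing are not tied to triplicates. ECG change is an Other endpoint in Part B and is not among the Part A endpoints. The QTc criteria in Protocol 7.1.2 are applied to a single reading and the investigator reviews every ECG, so participant monitoring does not depend on the table.

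A reader might also infer two stronger points that the documents do not support.

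- *Readings near the cut-points are the ones replaced by means.* The trigger is an investigator's judgement of clinical significance for any ECG abnormality. It is not linked to the table's thresholds.
- *Averaging cuts the within-occasion SD by the square root of 3.* That assumes independent errors among recordings made within 5 minutes. The documents give no QTcF variance, so no number of changed categories can be derived.

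**Conclusion.** The point holds as an error in the text of the SAP. Both QTcF category tables rest on a triplicate mean that no scheduled ECG in either part supplies: 0 of about 264 post-Baseline recordings, given full enrolment and no dropout. The change categories also lack a scheduled triplicate Baseline. The literal result is a table of triggered cases only; the likely practical result is single readings for most participants and means for the triggered ones. The number of participants affected cannot be estimated from the documents, because it depends on how many abnormalities are judged clinically significant.

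The consequence is limited to one supportive safety table. The documents do not support reading this as a threat to the primary PK analysis, to the TEAE endpoints or to participant safety. It is worth correcting because the rule is wrong as written and the correction is cheap.

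**What to change.** Make three changes in the SAP.

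1. In 5.5.3.3.1, replace the reference to triplicate means with: *based on the scheduled single recording*, for both the observed and the change categories.
2. State that 5.1.1.7 governs repeated and unscheduled values and takes precedence over the sentences on multiple observations in 5.1: the latest value before the first dose, the first value at each post-dose time point. Table 5-2 continues to set the Baseline day. If a Day 1 predose ECG is repeated, Baseline is then the last of those recordings, still one reading and not a mean. Confining the 5.1 rule to pre-dose values would not work, because 5.1.1.7 already prescribes the latest value there.
3. List triggered triplicates, with their mean, separately from the category table.

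The cost is a few sentences and one listing. No new data and no protocol change are needed, and no clinical rule is altered. Because 5.1 applies to all assessments, the precedence sentence should also be checked against the vital signs and laboratory summaries.
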